#### 9.2.1.3 Follow-Up of Subjects after Adverse Events (Serious and Non-Serious)

Unresolved events and post-study events will be followed up by telephone or with unscheduled visits at the discretion of the Investigator. These require evaluation and follow-up until the AE has been resolved or a reasonable explanation for its persistence is found.

#### 9.2.1.3.1 Unresolved Events

[figure not shown]
If an AE/SAE is present when the subject has completed the main study period, the course of the event must be followed until final outcome is known.

#### 9.2.1.3.2 Post-study Events

Any AE/SAE that occurs within 30 days after the end of the study should be reported. Such events will be included in the safety analysis of the study.

9.2.2	I		

Confidential Page 49 of 67

#### 9.2.3 Concomitant Medication and Physiotherapy Recording

Medications used at study entry (and within the prior 30 days) will be recorded at Screening . Thereafter, concomitant medications used will be recorded at each visit. At Screening , subjects will also be queried about their physiotherapy regimen and the nature and schedule recorded. At subsequent visits, subjects will be questioned by the Ashworth assessor whether or not there has been a change; the nature of any substantive changes is to be described.

#### 9.2.4 Vital Sign Measurement

Blood pressure and pulse will be measured at each clinic visit throughout study participation. Measurements will be made with the subject in a seated position (for at least 5 minutes). Results will be evaluated against pre-specified criteria for clinically significant change.

#### 9.2.5 Clinical Laboratory Testing

The following tests will be performed at Screening and Visit 7 (end of open-label fixed dose phase or upon early discontinuation):

#### Hematology:

- Red blood cell indices, including RBC count, hemoglobin, and hematocrit
- Total WBC count
- Differential WBC count
- Platelet count

#### Serum chemistry (Full Panel):

- Sodium
- Potassium
- Chloride
- $\bullet$  CO2
- Glucose (random)
- BUN
- Creatinine
- Calcium
- ALT

Confidential Page 50 of 67

- AST
- Alkaline phosphatase
- Total bilirubin
- Total protein
- Albumin

#### Urinalysis:

- Dipstick for pH, specific gravity
- Microscopic examination of the sediment
- Urine pregnancy test (for women) to be performed at Screening, and Visit 7 (Week 18) and Visit 11

Results for clinical laboratory parameters will be evaluated for clinically significant values according to pre-specified criteria. Laboratory tests may also be repeated between scheduled visits at the discretion of the Investigator. In addition, repeat testing should be performed at the end of the study to follow any clinically significant abnormality to resolution/stabilization.

#### 9.2.6 12-Lead ECG

ECG measurements will be collected in triplicate 2 minutes apart (except at Screening where only one measurement will be taken) and read by a central reader. The QTc data will be corrected using Fridericia's correction and Bazett's correction. In addition to the QT interval, the following parameters will be collected: PR interval, QRS, and ventricular rate; the presence of T-waves will be noted.

Clinically significant abnormalities will be reported as AEs.

[figure not shown]
#### 9.2.7 Physical Examination

Complete physical examination is to be performed at Screening and, as needed in response to changes in medical history, at the final study visit (Visit 11, or earlier in the event of premature termination). The complete examination will consist of evaluation of the skin, head, eyes, ears, nose, throat, neck, thyroid, lungs, heart, lymph nodes, abdomen, and extremities. Brief, targeted physical examinations are to be performed at other visits as necessary in response to clinically significant adverse events.

[figure not shown]
#### 9.2.8 Neurological Examination

Neurological examination sufficient to establish the EDSS score is to be performed at Screening. The examination is to consist of an evaluation of mental status; corneal reflexes; extra-ocular movements; facial sensation (light touch); facial strength; palatal movement; tongue movements; neck extension; neck flexion; head turning; respiration; forced vital capacity; tendon reflexes of the right and left biceps, triceps, supinator, quadriceps, and ankle (scored as 0=absent, 1=reduced, 2=normal, 3=increased, 4=clonus); and plantar stimulation (scored as 0=no movement or flexor; 1=extensor). Targeted examination is to be repeated, as needed in response to changes in medical history, at the final study visit (Visit 11, or earlier in the event of premature termination).

Confidential Page 51 of 67

Confidential Page 52 of 67

#### 10.3 Study Populations

#### 10.3.1 Efficacy Populations

#### 10.3.1.1 ITT Population

The ITT population will be defined as all subjects who are randomized to double-blind study drug at Visit 7 and subsequently received at least one dose of study medication.

#### 10.3.1.2 PP Population

The per protocol (PP) population will be defined as all subjects who are randomized to double-blind study drug at Visit 7, subsequently receive at least one dose of study medication, have at least one on-treatment assessment in Part 3, and do not have any major protocol violation (such as poor compliance). Protocol violations will be reviewed and subjects with major/minor violations will be

[figure not shown]
Confidential Page 53 of 67

identified prior to unblinding the clinical database. Subjects with a major protocol violation will be excluded from the analysis of the PP population.

In addition, concomitant medications will be reviewed for anti-spasticity medication use, its dose, and the timing relative to the in-clinic assessment. Adverse events will be reviewed in a similar fashion for confounding medical conditions. In-clinic Ashworth assessments that are judged to be potentially confounded will be flagged. The analysis of the PP population will exclude such potentially confounded assessments; response status will be solely on the basis of the clinician-rated CGIC.

Analyses of the primary efficacy endpoint will be repeated using the PP population if it differs in size from the ITT population in total number by more than 10% overall.

#### 10.3.2 Safety Population

#### 10.4 Statistical Methods

A detailed statistical analysis plan (SAP) will be written and finalized before the study starts. The plan will follow the outline of the statistical analyses including but not limited to points presented below, but details necessary to complete the statistical analyses will be given.

#### 10.4.1 Demographic and Other Baseline Characteristics

Descriptive summaries of the Safety Population will be prepared for the demographic and baseline (Screening) characteristics listed below. Categorical variables will be described with counts and percentages, ordinal variables with medians and quartiles, and interval variables with mean and 95% confidence interval (CI).

Descriptive comparisons will be made using the Pearson's chi-square test for categorical variables, Mann-Whitney U-test for ordinal variables, and Student's two-sample t-test for interval variables.

- Age (years)
- Gender
- Race/ethnicity
- Renal function (as estimated by calculated creatinine clearance)
- •
- •
- •

Confidential Page 54 of 67

[figure not shown]
Medical history at Visit 1 (prior conditions and present conditions) will be tabulated by body system, both with a summary of incidence by diagnosis and the numbers and proportions with any abnormality. A by subject listing will be created.

#### 10.4.2 Study Disposition and Dosing

The following descriptive summaries of study disposition and dosing will be provided.

#### 10.4.2.1 Subject Disposition Criteria

- Number of subjects who were enrolled in each phase of the study
- Number and proportion of subjects (by treatment group and overall) who discontinued the double-blind phase prior to Visit 11.
- Number and proportion of subjects (by treatment group and overall) who dropped-out for each of the following categories for why a subject may be prematurely discontinued from the study (Section 7.1.1):
  - Dropped-Out Due to Adverse Event: Subjects who are discontinued from the study medication due to the occurrence of an AE will be recorded as dropouts. The AE will be recorded and all subjects irrespective of time of dropout (after Visit 2 and have taken one study dose) will be considered for safety analysis.
  - Dropped-Out Due to Major Protocol Violation: Subjects who are discontinued from the study due to the occurrence of a major protocol violation will be recorded as dropouts.
     The protocol violation will be recorded and all subjects irrespective of time of dropout (after Visit 2 and have taken one study dose) will be considered for safety analysis.

 Dropped Due to Other Reasons: Subjects who are discontinued from the study due to any other reason will be recorded as dropouts. The reason for discontinuation will be recorded all subjects irrespective of time of dropout (after Visit 2 and have taken one study dose) will be considered for safety analysis.

Subjects who drop out after Visit 1 will not be replaced (Section 7.2).

Confidential Page 55 of 67

#### 10.4.2.2 Dosing

Dosing data at each visit will be summarized. Specifically, the numbers of subjects for each dose level and descriptive summaries (mean, median, and standard deviation) of dose at each visit will be provided. Individual subject listings will be prepared.

#### 10.4.3 Efficacy Analysis

#### 10.4.3.1 Primary Efficacy Analysis

The primary efficacy analysis will be performed using the intent-to-treat (ITT) population.

A subject will be classified as ,treatment failure" if the definition for failure (Section 10.1) is met at any time during the double-blind withdrawal period (Part 3).

The primary efficacy analysis will be carried out using a two-sided test at the alpha=0.05 level of

[figure not shown]
primary efficacy analysis will be carried out using a two-sided test at the alpha=0.05 level of significance.

#### 10.4.3.2 Additional Analyses of the Primary Efficacy Outcome

#### 10.4.3.2.1 Sensitivity Analyses

Severa	Several sensitivity analyses		
	The sensitivity analyses are as follows:		
(a)			
(b)			
(c)			
(d)			
(u)			

Confidential Page 56 of 67

[figure not shown]

Confidential Page 57 of 67

# 10.4.3.4.2 Subgroup Analyses Exploratory subgroup analyses will be performed to investigate the effect of the drug for different subgroups, those who used neurological concomitant medications those who used neurological concomitant medications score. 10.4.3.4.3 Sleep Interference Due to Spasticity 10.4.3.4.3.1 Awakenings Due to Spasticity 10.4.3.4.3.2 Hours of Sleep 10.4.3.4.4 Spasm Frequency

Confidential Page 58 of 67

The weekly mean of the daily spasm frequency will be computed using the average of the daily results that are obtained during the specified 7-day period. However, the weekly mean will be set to a missing value if a subject provides fewer than 3 days of data during the week.

#### 10.4.5 Safety Analysis

Safety parameters include AEs, daytime sedation, vital signs (resting pulse and sitting systolic and diastolic blood pressures), clinical laboratory tests, 12 lead ECG, physical examinations, neurological examinations and suicidality assessment.

#### 10.4.5.1 Adverse Events

All treatment-emergent adverse events (TEAE) will be coded in a standardized manner for regulatory activities. TEAEs will be coded according to body systems and preferred terms. A

Confidential Page 59 of 67

 
TEAE is defined as any event that only occurred after administration or that existed before drug administration but increased in severity or treatment attribution. For the randomized withdrawal phase, emergent events will be determined relative to the double-blind medication.
Adverse events reported as pre-existing at the start of the run-in or that emerge during the treatment phase will be considered pre-treatment adverse events. These will be summarized separately.
The incidence of TEAEs and SAEs will be summarized for the s (Part 2) and also by treatment group during the double-blind, par (Part 3). For each part, the incidence of TEAEs will be presented by system organ classification and preferred terms according to the Medical Dictionary for Regulatory Activities (MedDRA®), by causality, by severity, and by action taken. In addition, separate summaries will be prepared with subjects categorized by sex, age (below 65 years of age and 65 years of age and older), and race.
The effects of concomitant medications and/or medical conditions present at screening will also be explored. Should any medications be used by or conditions be present in 20% or more of the subjects overall, subjects will be categorized accordingly and the incidence of TEAEs in each par summarized. Additional drugs or diagnoses of interest may be identified during the blinded data review.
In addition, adverse events will be listed for all subjects, including verbatim and coded terms.
10.4.5.2

#### 10.4.5.3 Vital Signs

Sitting diastolic and systolic blood pressures and resting pulse measurements at each visit will be summarized using descriptive statistics (n, mean, standard deviation, median, minimum, and maximum) for measurements during the open-label phase and also by treatment groups during the randomized double-blind withdrawal phase. Similarly, change from Visit 1 at each visit will be summarized using descriptive statistics.

Values considered clinically significant by the Investigator are to be flagged. Criteria for possibly significant changes will be established *a priori*. Number and percentages of subjects with values of

Confidential Page 60 of 67

clinical significance will be summarized for each part; in Part 3, summaries will be by treatment group.

[figure not shown]
In addition, vital signs data will be listed for all subjects, inclusive of flags for whether the value is clinically significant in the Investigator's judgment and whether it meets pre-specified criteria as being possibly clinically significant.

#### 10.4.5.4 Clinical Laboratory Tests

Clinical laboratory testing (hematology, chemistry, and urinalysis) results at each visit (Screening and Visit 7) and its change from Screening (for all continuous clinical laboratory parameters) will be summarized using descriptive statistics (n, mean, standard deviation, minimum, median, and maximum).

Values outside laboratory normal range as well as those considered clinically significant by the Investigator are to be flagged as L (low) and H (high). Shift tables displaying the shift from laboratory normal range between Screening and Visit 7 will be generated. Criteria for possibly significant changes will be established *a priori* for selected parameters. The numbers and percents of subjects meeting these criteria will be summarized.

Clinical laboratory results will be listed for all subjects, inclusive of flags for whether or not the value is outside laboratory normal range, considered significant by the Investigator, or meet the prespecified criteria for being possibly clinically significant.

[figure not shown]

#### 10.4.5.6 Physical and Neurological Examinations

Descriptive statistics will be provided, by treatment group, for proportions of subjects with abnormalities on physical and neurological examinations. Physical and neurological examination

Confidential Page 61 of 67

findings will be listed. These will be reviewed for any emergent abnormalities that could be attributed to the new dosage form.

#### 10.4.6 Prior and Concomitant Medications

Prior and concomitant medications will be coded using WHODRUG and will be summarized using counts and percentages.

Neurological and anti-spasticity concomitant medications will be summarized separately for each treatment group using counts and percentages and will be listed for all subjects.

All recently used (within 30 days prior to Screening) concomitant medications will be listed for all subjects.

#### 10.5 Unblinding

Breaking of the blind will occur at completion of the study.

At completion of the study, breaking of the blind will occur once the database has been cleaned and locked. Prior to final database lock, any major protocol violations, including changes in medication use or physiotherapy, and changes in medical condition will be identified. Only at that time will the Sponsor be granted access to the unblinded data.

At all other timepoints, breaking of the blind for any subject is discouraged and should be performed only under medical emergency conditions where the identification of the subject's treatment assignment is critical for proper medical care to be administered. In such circumstances, the Investigator must contact the Sponsor's Medical Representative (or designee) for permission to unblind. The representative will be available 24 hours a day. If a decision is made to unblind a subject's assignment, the Investigator will call the IVRS/IWRS statistician and request the subject's treatment group. Only the Investigator and the IVRS/IWRS statistician will be unblinded to the subject's treatment group and they will be responsible for documenting the time, date, and reason for code break.

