## 6.5 Maintenance of Study Treatment Randomization Codes and Procedures for Breaking Codes

The randomization codes and blinding codes will be maintained by the statistician at the IVRS/IWRS. The randomization numbers and blinding codes generated will not be disclosed to any individual associated with reviewing the study documents.

The IVRS/IWRS will hold the only set of treatment codes and unblind individual subjects as required for regulatory reporting purposes. However, the Investigator, Sponsor, and study team will be kept blinded to treatment allocation. The treatment codes will be stored in a secure environment within the IVRS/IWRS and accessible only to the statistician.

The treatment code may be broken on an individual basis, in case of an SAE for which the Investigator must know the study agent identity to initiate appropriate treatment. The Investigator will be supplied with necessary information to break the study blind on an individual subject basis. If the study blind is broken, the Investigator must inform the medical monitor or designee and report the reason for unblinding. Date, time, and reason, together with the Investigator's signature, must be recorded. The site will contact the designated personnel from the IVRS/IWRS in case the treatment code needs to be broken.

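### Protocol 10.5 makes an emergency code break depend on the sponsor's permission, with no fallback, while the visible text of 6.5 has no permission step

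*Protocol*

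**What the plan says.** Two protocol sections describe how an individual treatment code is broken.

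**Protocol 10.5 (Unblinding).** Before study completion, breaking the blind is discouraged and should happen "only under medical emergency conditions where the identification of the subject's treatment assignment is critical for proper medical care". In that situation "the Investigator must contact the Sponsor's Medical Representative (or designee) for permission to unblind". On availability it adds: "The representative will be available 24 hours a day". The call to the IVRS/IWRS statistician comes next and is conditional: "If a decision is made to unblind a subject's assignment". Spread of the information is then limited: "Only the Investigator and the IVRS/IWRS statistician will be unblinded to the subject's treatment group". Those two are responsible for documenting the code break.

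**Protocol 6.5 (Maintenance of Study Treatment Randomization Codes and Procedures for Breaking Codes).** A code may be broken for an SAE "for which the Investigator must know the study agent identity to initiate appropriate treatment". It continues: "The Investigator will be supplied with necessary information to break the study blind on an individual subject basis". The site contacts designated IVRS/IWRS personnel. On the sponsor side, the duty is one of notice: "If the study blind is broken, the Investigator must inform the medical monitor or designee and report the reason for unblinding". The date, time and reason are recorded with the Investigator's signature.

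Neither section refers to the other.

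**The concern.** Section 10.5 first narrows code breaks to cases where knowing the assignment is critical for care. It then makes that knowledge depend on someone who is not treating the subject. It does not say what the Investigator should do if the representative cannot be reached, is slow to answer or does not agree.

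Part 3 compares continued treatment with down-titration to placebo, so the code tells a treating physician whether the subject is still on active drug or is being withdrawn from it. An Investigator who works from 6.5 would not learn that permission is expected. One who works from 10.5 could conclude that nothing can be done until it is given. At stake are timely care for the individual subject and uniform conduct across sites.

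**Working it through.** No arithmetic applies. The check sets the two sections side by side and then looks for text that reconciles them.

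1. **Trigger.** 6.5: an SAE for which the Investigator needs to know the agent in order to treat. 10.5: a medical emergency in which the assignment is critical for care. The triggers are worded differently, but both rest on clinical need.

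2. **Step before the code is released.** 6.5: none is stated beyond contact with IVRS/IWRS. 10.5: the sponsor's representative is contacted for permission, and the IVRS/IWRS call follows only once a decision to unblind has been made.

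3. **Who decides.** 6.5 frames the matter around the Investigator's need to know. 10.5 uses the word permission and then a passive construction that does not name the decision-maker. The natural reading is that the sponsor's agreement is needed.

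4. **Sponsor-side contact afterwards.** 6.5: the medical monitor or designee is informed and given the reason. 10.5: no separate notice is stated.

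5. **Fallback.** 10.5 offers 24-hour availability of the representative and nothing further. 6.5 has no permission step and so needs no fallback.

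6. **Can both be followed?** Yes, in order: obtain permission, call IVRS/IWRS, inform the medical monitor, sign the record. The difference is a precondition that appears in one section and is absent from the other.

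7. **Does other text remove the precondition?**
   - SAP 5.6 deals only with end-of-trial unblinding. The clause in SAP Section 2 that gives the SAP precedence therefore has no emergency code-break text to apply.
   - Protocol 11.5 exempts action against immediate hazards from the need for prior approval of a protocol change or deviation.
   - Protocol 11.5.1 covers emergency departures for one subject, with telephone contact when time allows. It does not mention unblinding. It treats the act as a departure that must be explained in the eCRF and reported in writing to the IRB/IEC.
   - Section 4.2.3 (Blinding) appears in the table of contents, but its text is not shown.

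In the visible text, then, an Investigator who breaks the code without permission has a route, but only as a departure from the protocol.

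**The case against.** The strongest case on the other side has four parts.

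**Silence is not conflict.** 6.5 nowhere says that permission is unnecessary, and its reference to supplying the Investigator with information may mean no more than the IVRS/IWRS contact route, since IVRS/IWRS holds the only set of codes. This stands. A reader might infer that the two sections contradict each other. They do not, because an Investigator can comply with both in sequence.

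**Refusal is not a stated rule.** A reader might infer that the sponsor holds a veto. That follows from the ordinary meaning of permission, but the documents describe no refusal process and do not say who makes the decision. What is shown is the narrower point that release depends on agreement and that no fallback is given. Round-the-clock availability answers much of the worry about delay. It does not remove the precondition.

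**Permission does help protect the blind.** A reader might think the step adds nothing because 10.5 already limits who learns the code. That limit controls spread after a break. Permission controls whether a break occurs at all. This has some weight here: the CGIC is rated by the treating physician (Protocol 4.1), who may be the unblinded Investigator, and a CGIC of 5 or more is one of the two components of treatment failure. This stands as the cost of the change.

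**Emergencies are already covered.** Sections 11.5 and 11.5.1 are general clauses, and their paperwork comes after the event and need not delay care. This is partly right. It still leaves a foreseeable safety action classed as a departure, and a site reading 10.5 is not directed to those clauses.

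**Conclusion.** The point holds as an inconsistency with a subject-safety consequence: in 10.5 an emergency code break depends on a sponsor decision without a fallback, and the visible text of 6.5 has no such step. It is worth correcting because the correction is cheap.

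Its size is not quantified. The documents give no rate of emergency code breaks, nor of delayed or refused ones. Exposure is confined to subjects who need such a break in the 4-week Part 3, for which at least 240 randomized subjects are planned. The primary analysis method is unaffected.

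The conclusion assumes that no unseen text supplies a reconciling rule. Section 4.2.3 (Blinding) is a natural place for one and is not shown, so confidence is moderate. A reader might also infer that code release itself is not covered around the clock, since the 24-hour statement concerns only the representative. The documents do not show this, and it is a question for the sponsor.

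**What to change.** In Protocol 10.5, replace the permission wording with the following rule:

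- The Investigator makes the final decision, and may request the code directly from the designated IVRS/IWRS personnel when it is needed for urgent care.
- The sponsor's representative is consulted first if time permits.
- The medical monitor is informed promptly afterwards, and the date, time, reason and Investigator's signature are recorded.

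Keep the restriction to emergencies and the limit on who learns the treatment group. Cross-refer 6.5 and 10.5, and check Section 4.2.3 against the revised rule. Separately, ask the sponsor to confirm that IVRS/IWRS can release a code at any hour.

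The cost is a few sentences in an amendment and a memo to sites, with no change to sample size or analysis. The downside is that the sponsor loses a prior check on unnecessary code breaks and can question one only afterwards. This matters modestly, because an unblinded Investigator may also rate the CGIC. The signed record would show which later ratings could be affected.
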